Clinicians often note that both intraoperatively, and months postoperatively, mastectomy flaps are clinically cool to the touch, but mastectomy flap temperature has not been objectively studied. The importance of maintaining normothermia during surgery has been well established in both anesthesia and surgical specialties literature over the past twenty years. The combinations of impaired thermoregulatory control from the anesthesia and exposure to cool operating rooms makes most surgical patients hypothermic (defined by anesthesia practitioners as being less than or equal to 36 degrees celsius.) Wound temperature is heavily reliant on, and correlated with, core body temperature, as the wound temperature is higher in normothermic patients than in hypothermic patients. The clinical impact of this has most markedly been observed in the colorectal specialty in which a study found that patients with mild perioperative hypothermia had three times as many surgical-wound infections as the normothermic patients. As stated above, implant-based reconstruction after mastectomy consistently has higher rates of infection than other implant based procedures or even autologous breast reconstruction. This is often attributed to the decreased mastectomy flap perfusion that becomes solely reliant upon the subdermal plexus after a total mastectomy ultimately leading to impaired blood flow and subsequent impairment in immune function.

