Given the increasing quantity of literature that concludes that core temperature is an independent risk factor for increased complications there has been an attempt to control this by preconditioning the mastectomy flaps. Five to thirty percent of mastectomy skin flap necrosis is often cited in the literature. While in its infancy, the handful of studies that have attempted this intervention have found promising outcomes. One review article examined the concept of thermal preconditioning which was defined as "local or systemic supraphysiological heating of an organism or specific organ before an environmental insult." It has been established that through heat exposure there is an increase in heat shock proteins (HSP). Specifically, HSP-32 can catalyze hemoglobin to biliverdin and iron with a byproduct of this reaction being the local release of carbon monoxide. Carbon monoxide is a potent vasodilator that causes an increase in vascularity to the specific preconditioned area. HSP-70 is also suspected to play a role in vasodilation through inducing production of nitrogen oxide synthase (iNOS). Protective effects of HSP and preconditioning has been demonstrated in multiple other organs like kidneys, bone, heart and liver. This physiologic reaction was examined in a randomized control trial through local supraphysiologic heating of breasts that were to undergo mastectomy the following day. A heat source of 43 degrees Celsius was applied for 30 minutes 3 times with a 30-minute rest between the repetitions. It was found that those who did not undergo preconditioning had 35% necrosis rate of mastectomy flaps, while those who did undergo preconditioning experienced 26% necrosis rate of mastectomy flaps.

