## 6.0 STATISTICAL CONSIDERATIONS

### 6.1 General Design Issues

This is a non-randomized prospective observational pilot study.

1. **Primary Hypotheses:** We hypothesize that at least 60% of eligible patients will consent to having flap temperatures measured intraoperatively, and that we will successfully measure all relevant temperatures (12 per breast) on at least 90% of those consenting. Both of these measures must be achieved to deem a future study feasible.
2. **Secondary hypotheses:** We hypothesize that we will observe a significant difference between average mean flap temperature and average core body temperature.
3. **Exploratory analyses:** We will describe post-surgical complications over the 90-day post-surgery period as frequencies.

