### **6.3 Data Analyses**

This study will provide quantitative data on consent (proportion of all eligible patients approached who consent to having flap temperatures measured intra-operatively), and on ability to successfully measure all 12 flap temperatures (per breast) on patients who have consented.

We will calculate 95% confidence intervals for each of the above feasibility measures to determine the range of estimates that are consistent with our data. We will use one-sample tests of binomial proportions to compare the consent and successful measurement proportions to the hypothesized values of 60% and 90%, respectively.

We will examine intra-individual variability in flap temperature measurements by quadrant and by breast; we expect these sources of potential variability to be weak, controlling for time point of measurement (pre vs post mastectomy vs pre-implantation). We will derive average flap temperatures for each of the three time points separately. We will compare average flap temperatures at each of the three time points during surgery to average core body temperature at that time, using paired t-tests for the differences in means in a single sample. Our hypothesis is that, across all three time points, average flap temperatures will be lower than average core body temperatures, and that as time goes on during surgery, from pre- to post-mastectomy to pre-implantation, we expect average flap temperatures will be lower than average core body temperatures by a larger degree, as we expect flap temperatures to cool more quickly during surgery than overall body temperature.

In our exploratory analyses, we will document the occurrence and major and minor wound/surgical complications over the 90-day period following surgery and will examine whether there is a relation between the number of such complications per patient and 1. the patient's magnitude of difference between average flap temperatures and core body temperatures, and 2. the patient's absolute average flap temperatures .

.

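### The exploratory complication analysis uses two flap exposures without a core-temperature term, so neither one alone separates a flap association from a core association

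*Combined protocol and SAP*

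**What the plan says.** Section 6.3 says that the study "will examine whether there is a relation between the number of such complications per patient" and, first, the "magnitude of difference between average flap temperatures and core body temperatures" and, second, the patient's "absolute average flap temperatures". It names no model or covariate and does not say whether the two exposures are analysed separately or together. Section 6.1 describes the same exploratory work more modestly: "We will describe post-surgical complications over the 90-day post-surgery period as frequencies".

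Section 1.0 gives core temperature two roles. On the exposure side: "Wound temperature is heavily reliant on, and correlated with, core body temperature". On the outcome side, it reports a growing literature concluding that "core temperature is an independent risk factor for increased complications", and it cites a colorectal study in which "patients with mild perioperative hypothermia had three times as many surgical-wound infections as the normothermic patients".

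Section 5.1 has core temperature recorded whenever flap temperatures are taken, so the data for an adjusted analysis are already planned.

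**The concern.** A variable related to both the exposure and the outcome is a confounder, and by the protocol's own account core temperature is related to both. The plan uses core only inside a subtraction. A gap (core minus flap) makes core and flap act with equal and opposite effects, whereas the background gives them the same direction: colder is worse for each.

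Section 1.0 asks whether women with cooler flaps have more complications, in the hope that the pilot data will support later trials of flap warming or preconditioning. Section 5.1.2 says that core temperature is already managed as standard care. A later flap trial therefore needs to know whether the flap carries information beyond core. An association that is partly a core association, or a flap association hidden by the subtraction, could be carried forward wrongly.

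**Working it through.** **The plan's own figures.** None is stated for the exploratory analysis. The number available comes from Section 6.2: 0.60 × 30 = 18 women. The precision given there reproduces with exact binomial intervals. For 18/30 the interval is 40.6% to 77.3%, so the lower distance is 60.0 − 40.6 = 19.4 points; for 16/18 the lower bound is 65.3%. None of this depends on the point made here.

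**Arithmetic on the exposures.** Take two women with flap 33 °C.
- Core 35 °C (hypothermic by the 36 °C threshold in Section 5.1.2): gap = 35 − 33 = 2.
- Core 37 °C: gap = 37 − 33 = 4.

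The hypothermic woman has the smaller gap and the same absolute flap temperature. Neither exposure shows the core risk that Section 1.0 describes.

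**Direction and size of bias.** Let C be core and F flap, with F = a + bC + e across patients. Let the log complication rate be −gC·C − gF·F, up to a constant, and let D = C − F.

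- Var(D) = (1−b)²·sC² + sE².
- Slope on D without core = gF − (1−b)·sC²·(gC + gF) / Var(D).
- Slope per °C cooler flap without core = gF + gC·b·sC² / (b²·sC² + sE²).
- With C in the model, the slope on D, or per °C cooler flap, is gF.

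The bias in D is negative for b < 1, zero at b = 1 and positive for b > 1.

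Assumed inputs, not in the documents: sC = 0.5 °C, residual flap SD sE = 1.0 °C, gF = 0.30. The three-fold core effect is spread over 2 °C (gC = ln 3 / 2 = 0.549) or 1 °C (gC = 1.099). Section 1.0 gives the three-fold figure without a temperature separation.

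| Slope b | Gap alone, gC 0.549 | Gap alone, gC 1.099 | Flap alone, gC 0.549 | Flap alone, gC 1.099 |
|---|---|---|---|---|
| 0 | 0.13 | 0.02 | 0.30 | 0.30 |
| 0.5 | 0.20 | 0.14 | 0.37 | 0.43 |
| 1 | 0.30 | 0.30 | 0.41 | 0.52 |
| 1.5 | 0.40 | 0.46 | 0.43 | 0.56 |

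Worked cell (b = 0, gC = 0.549): 0.30 − (1 × 0.25 × 0.849) / 1.25 = 0.30 − 0.17 = 0.13.

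Over core SD 0.3 to 0.8, residual flap SD 0.5 to 1.5 and b of 0 to 0.5, with a core effect present, the gap slope runs from 0.28 down to −0.79. The sign can therefore reverse. In 300,000 simulated patients, with b of 0, 0.5 and 1, Poisson regression including core returned 0.298 to 0.304 against the true 0.30.

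**If only core matters.** With core SD 0.5 and total flap SD 1.0, the correlation of the gap with risk is −(0.5 − r)/√(1.25 − r), where r is the core–flap correlation. It is −0.45 at r = 0, −0.21 at r = 0.3, 0 at r = 0.5 and +0.27 at r = 0.7.

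In simulated pilots of 18 women averaging 0.5 complications each, unadjusted flap temperature can pick up a core-only effect. The table gives the share significant in the hypothesised direction (nominal 2.5%). Ranges cover separate simulation runs.

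| r | Rate ×3 per 1 °C of core | Rate ×3 per 2 °C of core |
|---|---|---|
| 0.3 | 6% | about 4% |
| 0.5 | 9–11% | about 5% |
| 0.7 | 16–17% | about 7% |

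Adjusting for core by partial rank correlation brings the one-degree scenario back to about 2–3%.

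**The case against.** A reader might infer that a hypothermic core generally lowers the gap, so that a larger gap will look protective. The documents do not support that. It is exact at a fixed flap temperature, but on average it requires flap to fall by less than 1 °C per 1 °C of core across patients, and no slope is given. Section 6.3 adds that "we expect flap temperatures to cool more quickly during surgery than overall body temperature". That describes change within surgery, not the slope between patients, so it does not settle the question, but it gives no support for a slope below 1 either. This objection stands in full: the direction of bias in the gap is unknown.

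The sizes also rest on assumed inputs. Section 5.1.2 has core hypothermia actively corrected, which plausibly narrows the spread of core and shrinks the bias. This stands; the figures are illustrations.

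The plan does not rule out adjustment. Because core = gap + flap, entering both exposures in one model would condition on core. Section 6.3 does not promise this, so the objection limits the criticism to an omission.

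The stated aim can be read as descriptive, and absolute flap temperature answers a descriptive question directly. BMI, smoking, diabetes and radiation are not adjusted for either. That is fair, but core is the one variable that the plan builds into an exposure and that the background ties to both sides.

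Finally, little can be settled with about 18 women. By the Fisher z approximation, 80% power at two-sided 5% needs a correlation of about 0.62. In simulation, a flap effect of 0.30 was detected in about 7–10% of pilots with core adjustment and, with no core effect present, in about 11–12% without it. This stands, and it argues for descriptive reporting whichever analysis is used.

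**Conclusion.** The point holds as an omission in the exploratory analysis. Taken alone, neither planned exposure separates a flap association from a core association. Absolute flap temperature absorbs part of any core effect when flap tracks core (0.37 to 0.43 against a true 0.30 at a slope of 0.5). The gap is attenuated or reversed below a slope of 1, unbiased at 1 and inflated above it. These sizes depend on assumed spreads, slope and core effect; the structure of the bias follows from the subtraction and from the protocol's own account of core temperature.

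Two stronger readings are not supported. The gap need not be dropped: it is a legitimate quantity and keeping it is a matter of choice, provided it is not read alone as a flap effect. Nor are the pilot's main conclusions at risk: feasibility rests on consent and measurement success, and Section 6.2 ties the power of a later study to flap–core temperature differences, not to this association.

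**What to change.** In Section 6.3, alongside the two planned exposures:

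- Add an analysis of complications on flap temperature adjusted for the core temperature recorded at the same time point. A partial rank correlation would do, or one count model with both terms.
- Report core temperature's own association with complications.
- Keep the flap–core difference, state its sign and the time point used, and say that it will not be interpreted alone as a flap effect.
- Report all of these as estimates with intervals, labelled descriptive, and bring Section 6.1 into line, since it mentions only frequencies.

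The cost is a few sentences, one degree of freedom and a slightly wider interval in an analysis of about 18 women. No new data are needed, and the sample size and feasibility criteria stay as they are.

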## **Mastectomy Flap Temperature and Clinical Implications**

Wake Forest Baptist Comprehensive Cancer Center

WFBCCC # 74222

Additionally, we will explore the relation between average mastectomy flap temperature and number and degree of post-surgical complications for up to 90 days post-surgery, to examine whether patients with cooler mastectomy flaps intraoperatively have increased surgical complications compared to patients with warmer flaps. While there is a possibility that the presence or absence of cancer can affect surgical complication rates, we do plan to include patients undergoing both therapeutic and prophylactic mastectomy in this study. When performing data analysis, complications are recorded by breast rather than by patient allowing us to note which breasts undergo mastectomy for therapeutic reasons and which are prophylactic.

If we are successful in showing feasibility in our primary objectives, we hope that these pilot data will ultimately aid in future, large interventions designed to warm or precondition mastectomy flaps in efforts to optimize surgical outcomes for implant based breast reconstruction surgeries.

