## **4.0 Study Outcomes and Study Measures**

### **4.1 Primary Outcomes**

5.1.1 The proportion of eligible women who consent to having mastectomy flap temperatures measured during surgery will be computed by dividing the total number of eligible women screened by the number of these women who consent. We will compute a 95% confidence interval around this proportion.

5.1.2 We will compute the proportion who successfully have all relevant flap temperatures measured (this will either be 12 or 24 total expected flap temperatures: 4 quadrants, at three time points- pre and post-mastectomy and pre-implant placement; one or both breasts), and we will compute a 95% confidence interval around this proportion.

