### **4.3 Exploratory Outcome**

Mastectomy flap compromise/wound breakdown (major vs. minor complication) will be assessed over 90 days following surgery. We will document the following through chart review including but not limited to infection, ischemia, seroma, hematoma, and wound dehiscence.

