## **Mastectomy Flap Temperature and Clinical Implications**

Wake Forest Baptist Comprehensive Cancer Center

WFBCCC # 74222

	

- Post-mastectomy - core temp and flap temp in 4 quadrants

- Pre-implant placement – core temp and flap temp in 4 quadrants

Postoperative	

- Duration of drains

- Seroma formation

- Infection within 90 days

- Antibiotic administration postoperatively, up to 90 days

- Mastectomy flap necrosis within 90 days

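### The complication analysis in section 6.3 works with per-patient counts and patient-level average temperatures, so the quadrant and breast contrasts already measured go unused

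*Combined protocol and SAP*

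**What the plan says.** **Temperature.** Section 4.1 sets out the readings: "4 quadrants, at three time points- pre and post-mastectomy and pre-implant placement; one or both breasts", giving 12 in a unilateral and 24 in a bilateral case. Table 1 in section 5.1 repeats this for each time point, for example "Post-mastectomy - core temp and flap temp in 4 quadrants".

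**Complications.** Section 4.3 states: "Mastectomy flap compromise/wound breakdown (major vs. minor complication) will be assessed over 90 days following surgery". It continues: "We will document the following through chart review including but not limited to infection, ischemia, seroma, hematoma, and wound dehiscence". Table 1 has the item "Mastectomy flap necrosis within 90 days". None of these items names a place within the flap. The finest unit named anywhere is the breast; the closing part of section 1.0 says that "complications are recorded by breast rather than by patient".

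**Analysis.** Objective 2.3.1 is to relate flap temperature to complications within 90 days. Section 6.3 does this with a complication count per patient, set against the patient's average flap–core difference and the patient's "absolute average flap temperatures". Averages are formed separately at each of the three time points, but the section does not say which one enters the complication analysis. Variability by quadrant and by breast is to be examined, with the remark that "we expect these sources of potential variability to be weak". No step follows if it proves not to be weak, and no step links a quadrant's temperature to an event in that quadrant.

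**The concern.** Ischemia, necrosis and dehiscence happen at a place on the flap, and the study places a probe in each quadrant. The planned analysis then discards place on both sides: the exposure is averaged over quadrants and breasts, and the outcome is summed over breasts.

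This has three consequences:

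- A local cold area is diluted in the exposure.
- In a bilateral patient, a cold flap with a complication and a warm flap without one become one intermediate temperature and one count. Such a patient also has two flaps at risk, so her count can be higher for that reason alone. The per-patient count also departs from the by-breast recording announced in section 1.0.
- The only comparison left is between about 18 women who differ in BMI, smoking, diabetes and prior radiation, too few for adjustment.

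The temperatures are kept and can be re-analysed later. The site of a complication can be recovered later only if the clinic note happened to record it, so the time to ask for it is before chart review.

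**Working it through.** **Inputs**

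- Readings averaged at one time point: k = 4 (unilateral) or 8 (bilateral), from section 4.1. Over three time points: 12 or 24.
- Expected participants: 18, from section 6.2. This reproduces as 0.60 × 30 = 18. The plan gives no figure of its own for dilution or for the number of complications.
- Breasts: 18 × 1 = 18 to 18 × 2 = 36. The mix of unilateral and bilateral surgery is not given, so both extremes are shown.
- Flap necrosis: 5% to 30%, cited in section 1.0. Treating it as a rate per breast is an assumption.
- Depth d of a cold quadrant below the others: not given. A range of 2 to 4 °C is assumed.

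**Step 1: dilution at one time point.** If one quadrant lies d below the others, the average falls by d/k.

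| Case | Formula | d = 2 °C | d = 4 °C |
|---|---|---|---|
| Unilateral | d/4 | 0.50 °C | 1.00 °C |
| Bilateral | d/8 | 0.25 °C | 0.50 °C |

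**Step 2: if the time points are pooled.** Suppose the quadrant is cold only at the two later time points and all readings are averaged. The shift is 2d/12 = 0.33 to 0.67 °C (unilateral) or 2d/24 = 0.17 to 0.33 °C (bilateral).

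**Step 3: within the flap.** The affected quadrant minus the mean of the other three equals −d, the full 2 to 4 °C, if the affected quadrant is the cold one.

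**Step 4: merging two flaps.** If a bilateral patient's flaps differ by D on average, her patient average lies D/2 from each. With a per-breast necrosis rate r, the expected number of necrotic flaps is r for a unilateral and 2r for a bilateral patient: 0.05 to 0.30 against 0.10 to 0.60 over the cited range, with no difference in temperature needed.

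**Step 5: expected necrosis events.** Lowest: 18 × 0.05 = 0.9. Highest: 36 × 0.30 = 10.8. So about 1 to 11 flaps.

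**Step 6: can a test be attached?** A natural reference is that the affected quadrant is the coldest of four by chance with probability 1/4. With one event the smallest attainable one-sided p is 0.25; with two it is 0.25² = 0.0625. An event covering two quadrants changes the chance that the coldest is among them to 2/4 = 0.50, so one reference value does not fit all events. The value 1/4 also presumes that the quadrants are alike in all other respects, which they need not be.

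**The case against.** The strongest defence is that section 1.0 poses a question between patients: do women with colder flaps fare worse than women with warmer ones? Section 6.3 answers that question. The background is led by infection and by hypothermia of the whole body or whole flap, and infection, seroma and hematoma often have no single quadrant. The objective is exploratory, the pilot is sized for feasibility, and section 6.1 promises only frequencies of complications. All of this stands. It limits the weight of the point and confines the quadrant question to localisable events. It does not explain why complications recorded by breast are then analysed per patient.

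The defence can also say that location is not ruled out. Section 5.1 leaves the data list open, section 4.3 does the same for complications, and section 8 names a Post-Operative Data Collection Form whose contents are not shown. That is correct: location is unplanned, not excluded.

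A reader might infer more than the documents support:

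- *That the within-flap comparison is free of confounding.* It is not. Flap thickness, incision or tumour site and local perfusion vary by quadrant, and poor local perfusion could produce both the cold reading and the necrosis.
- *That the exposure is a single patient average and the quadrant signal is lost.* There are two exposures, one of them relative to core temperature. Averages are formed at three time points, quadrant readings are kept and their variability is examined. The signal is diluted, not erased.
- *That this pilot could test whether the cold quadrant is the one that fails.* Any such claim depends on an event count and a match rate that the documents do not supply.

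**Conclusion.** The point holds as an inexpensive improvement to the exploratory analysis. As written, section 6.3 leaves quadrant and breast contrasts unused for objective 2.3.1, and the plan cannot compare the affected part of a flap with the remainder of that flap because no complication item states a quadrant.

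The fractions 1/4 and 1/8 follow from the design. The temperature shifts rest on the assumed 2 to 4 °C, and the plan itself expects quadrant differences to be weak; if they are, little is diluted. The figure of about 1 to 11 events rests on reading 5% to 30% as a per-breast rate and on 18 to 36 breasts. Dehiscence could add localisable events, but the documents give no rate for it. On these numbers the within-flap comparison can describe, and cannot test.

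**What to change.** 1. **Chart review.** For each localisable complication (ischemia or necrosis, dehiscence), record the breast and the quadrant(s) affected. List other events as unlocalised. Keep cellulitis at the probe site separate, since section 7.1 names it as a possible adverse event of the probe.
2. **Section 6.3, unit of analysis.** Analyse complications by breast with clustering by patient, in line with section 1.0, and state which time point's average is used.
3. **Section 6.3, exposure.** Report the coldest-quadrant temperature per breast beside the average.
4. **Section 6.3, within-flap description.** For each localised event, give the mean pre-implant temperature of the affected quadrant(s) minus the mean of the unaffected quadrants of the same breast. Label it descriptive, with no significance test or power claim. State that it removes factors shared by the flap (BMI, smoking, diabetes, core temperature) but not factors that differ by quadrant.

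The cost is one chart-review item and a short addition to section 6.3; no new measurement is needed. The downside is that some notes will not localise the event and that events will be few.
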